5.2.12. T2- Telephone contact at D98 (± 1 day)

This phone call between patients (or their parents) and the investigator (or his/her deputy) will

allow to record all adverse events having occurred since the latest visit (AE recorded at visit

V10).

The investigator should assess the efficacy and tolerance and the dose of treatment should be

adjusted accordingly, when applicable.

In opinion of investigator, the dose could be re-adjusted according the effectiveness/tolerability

of treatment to patient.

In case of need, it is to plan a visit on site within the week following phone contact for obtaining

new bottles of treatment with the corresponding dose.

The other doses decrease, from 40 to 20 and 10 to 5 mg, in agreement with investigator don't

need a visit. The bottles contain a suitable number of tablets to decrease the dose.

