BIOPROJET Version 3.0 Protocol P11-06/ BF2.649 September 30th, 2020 EudraCT number: 2013-001506-29

6 treatment daily dose regimens are available: 5mg, 10mg, 15mg, 20mg, 30mg and 40mg/d from the visit 10 until the end of study.

T2 - Telephone contact at D91 (± 1 day)

During this telephone contact:

- The investigator should assess the efficacy and tolerance.

In opinion of investigator, if patient needs a dose adjustment, the dose could be re-adjusted according the effectiveness/tolerability of treatment to patient.

In case of need, it is possible to plan a visit on site within the week following phone contact for obtaining new bottles of treatment with the corresponding dose.

- Record all adverse events that have occurred.

V11 - Dose adjustment visit (D112 \pm 7 days)

Idem to the visit V9

V12 - Dose adjustment visit (D196 \pm 7 days)

Idem to the visit V11

V13 - Dose adjustment visit (D364 \pm 7 days)

Idem to the visit V12 + a blood sample will be taken for routine haematological and biochemical test (including β -HCG pregnancy test for pubescent female) and semi-quantitative urinalysis (dipstick).

All subsequent visits are performed each 6 months.

Idem to the visit V13

Phone visits during the COVID-19 pandemic

In order to limit the risk for the patient to spread/acquire the infection, special measures are put in place to maintain the participants in the study. The investigator should assess during these calls the efficacy and tolerance and the dose of treatment should be adjusted accordingly, when applicable.

Direct shipment of study treatment from the site, or hospital pharmacy, to the patient's home is allowed via a courier with the full documentation of shipment and receipt by the patient/parents. Patients will return all medication at his/her subsequent site visit. Diaries to be documented daily are sent to the patient with the study treatment.

Study Duration and planned dates

[figure not shown]
The actual overall study duration or patients recruitment period may vary according to the number of screened patients presenting the main inclusion and exclusion criteria.

Study duration for each patient: 13 weeks (2 week of wash-out + 2 weeks for baseline + 8 weeks under double blind study treatment + 1 week for study treatment wash-out). Followed by a prolonged open-label period. Planned dates for the Clinical Study: Start O1 2016

P11-06 Study Design – Part 1 Double Blind Period

Double-Blind period

Single-Blind period

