- 7 In case of dose decrease, an unscheduled visit should be planned within the week following the phone contact in order to decrease the dose from 20 to 10 mg. The other doses decrease, from 40 to 20 and 10 to 5 mg, don't require a visit.

ABBREVATIONS USED IN THE PROTOCOL

AEs Adverse events

ALAT Alanine aminotransferase

ANCOVA Analysis of Covariance test

ASAT Aspartate aminotransferase

AUC Area under the concentration-time curve

BMI Body mass index

CASS Child and Adolescent Sleepiness Scale

CDI Childhood Depression Inventory

CGI-C Clinical Global Impression of Change

CGI-S Clinical Global Impression of Severity

Cmax Maximum observed concentration

CNIL Commission Nationale de l'Informatique et des Libertés

CNS Central nervous system

CRF Case report form

CRO Contract Research Organization

CSF Cerebral Spinal Fluid
CSR Clinical Study Report

C-SSRS Columbia-Suicide Severity Rating Scale

DMB Data Management Book

DSM-IV Diagnostic System Medical, fourth version

DSMB Data Safety Monitoring Board

ECG Electrocardiogram

EDS Excessive Daytime Sleepiness

FAS Full Analysis Set

GCP Good Clinical Practice

GGT Gamma glutamyltransferase
GMP Good Manufacturing Practice

H3R Histamine H3 receptor

ICH International conference on harmonization of technical

requirements for registration of pharmaceuticals for human use

ICSD International Classification of Sleep Disorders

IEC Independent Ethics Committee

IRB Institutional Review Board

BIOPROJET Version 3.0
Protocol P11-06/ BF2.649 September 30th, 2020
EudraCT number: 2013-001506-29

KO Knock-out

MSLT Multiple Sleep Latency Test

MWT Maintenance of Wakefulness Test
NOAEL No observable adverse effect levels
OSA Obstructive Sleep Apnoea syndrome

PDSS Pediatric Daytime Sleepiness Scale

PS Paradoxical sleep
PSG Polysomnography

REM Rapid Eye Movement
SAE Serious Adverse Event

SD Standard Deviation

TEA-Ch Test of Everyday Attention for Children

ß-hCG Human chorionic gonadotropin

SWS Slow Wave Sleep
Tmax Time to Cmax

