- From Week 13: according to the investigator's prescription patients for whom the optimal dose level is estimated will continue at the same dose or if not sufficiently improved in their symptoms, and with a good tolerance, will increase to a higher dose or the level dose will be reduced based on the tolerance to the product.

BF2.649 at 5 mg/day: 1 tablet of BF2.649 5 mg in the morning during 28 days, or

BF2.649 at 10 mg/day: 2 tablets of BF2.649 5 mg in the morning during 28 days, or

BF2.649 at 15 mg/day: 3 tablets of BF2.649 5 mg in the morning during 28 days, or

BF2.649 at 20 mg/day: 1 tablet of BF2.649 20 mg in the morning during 28 days, or

BF2.649 at 30 mg/day: 2 tablets of BF2.649 5 mg and 1 tablet of BF2.649 20 mg in the morning during 28 days, or

BF2.649 at 40 mg/day: 2 tablets of BF2.649 20 mg or placebo in the morning during 28 days. Treatment dosage at 40mg/day not allowed for patient with a weight less than 40 kg.

At D91 during the phone contact the dose will be reduce in case of poor tolerance, when applicable.

$-V11 (D112\pm 2)$:

According to the investigator's prescription patients for whom the optimal dose level is estimated will continue at the same dose or if not sufficiently improved in their symptoms, and with a good tolerance, will increase to a higher dose or the level dose will be reduced based on the tolerance to the product.

BF2.649 at 5 mg/day: 1 tablet of BF2.649 5 mg in the morning during 3-month, or

BF2.649 at 10 mg/day: 2 tablets of BF2.649 5 mg in the morning during 3-month, or

BF2.649 at 15 mg/day: 3 tablets of BF2.649 5 mg in the morning during 3-month, or

BF2.649 at 20 mg/day: 1 tablet of BF2.649 20 mg in the morning during 3-month, or

BF2.649 at 30 mg/day: 2 tablets of BF2.649 5 mg and 1 tablet of BF2.649 20 mg in the morning during 3-month, or

BF2.649 at 40 mg/day: 2 tablets of BF2.649 20 mg or placebo in the morning during 3-month. Treatment dosage at 40mg/day not allowed for patient with a weight less than 40 kg.

 $-V12 (D196\pm 2)$:

According to the investigator's prescription patients for whom the optimal dose level is Confidential 68

estimated will continue at the same dose or if not sufficiently improved in their symptoms, and with a good tolerance, will increase to a higher dose or the level dose will be reduced based on the tolerance to the product.

BF2.649 at 5 mg/day: 1 tablet of BF2.649 5 mg in the morning during 6-month, or

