5.2.11. V9- Dose adjustment visit (Day 77± 2 days)

A complete interrogation including occurred of possible adverse events and concomitant

medication used will be done and recorded.

A physical examination including vital signs shall be carried out,

12-lead ECG recording with calculation and control of QTcF,

The following questionnaires should be performed:

- PDSS,

- CGI-C on EDS and on cataplexy,

- CDI,

- C-SSRS,

- Patient's Global Opinion on the effect of investigational treatment if able to express himself.

If not will be reported either by parents or teachers,

- Retrieval of sleep diary. (Sleep diary will be filled out daily during the 7 days prior to the next

visit) and delivery of one other.

Investigational treatment allocation: the dose of pitolisant will be individually adjusted

according to the investigator's prescription patients for whom the optimal dose level is

estimated will continue at the same dose or if not sufficiently improved in their symptoms, and

with a good tolerance, will increase to a higher dose or the level dose will be reduced based on

the tolerance to the product. Dose allocation: either 5, 10, 20 or placebo in the morning during

7 days.

EudraCT number: 2013-001506-29

The treatment pack bring back from previous visit by patient is checked by investigator for the compliance. Investigator will remind patient to bring back the investigational treatment packs

Version 3.0

at the next visit.

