5.2.13. V10- Dose adjustment visit (Day 84 ± 2 days)

Idem to the visit V9.

Investigational treatment allocation: the dose of pitolisant will be individually adjusted

according to the investigator's prescription.

A blood sample will be taken for routine haematological and biochemical test (including β-

HCG pregnancy test for pubescent female) and semi-quantitative urinalysis (dipstick),

Dose allocation: either 5, 10, 15, 20, 30 or 40 mg/day or placebo in the morning during 28 days.

Patients with a weight less than 40 kg could be treated with a maximum daily dose up to 20 mg.

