5.2.14. V11- Dose adjustment visit (Day 112 \pm 7 days)

Idem to the visit V9.

Dose allocation: either 5, 10, 15, 20, 30 or 40 mg/day or placebo in the morning during 3-month.

Patients with a weight less than 40 kg could be treated with a maximum daily dose up to 20 mg.

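### Protocol section 5.2.12 dates the open-label phone contact T2 at D98 ± 1 day, while three other places in the protocol give D91

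*Protocol*

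**What the plan says.** Four places in protocol version 3.0 date the open-label telephone contact T2:

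- Section 5.2.12, in the visit-by-visit procedures: "T2- Telephone contact at D98", ± 1 day.
- Synopsis, study design and conduct: "T2 - Telephone contact at D91", ± 1 day.
- Part 2 open-label time and events schedule: study day D91, ± 1 day.
- Section 4.2, dosage regimen: "At D91 during the phone contact the dose will be reduce in case of poor tolerance, when applicable".

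The neighbouring visits show what the call is for. At V9 (D77), section 5.2.11 stops at 20 mg: "Dose allocation: either 5, 10, 20 or placebo in the morning during" seven days. At V10 (D84), section 5.2.13 opens the full range: "Dose allocation: either 5, 10, 15, 20, 30 or 40 mg/day or placebo in the morning during 28 days", with a ceiling of 20 mg/day for patients under 40 kg. The next scheduled visit after T2 is V11 at D112 (section 5.2.14).

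Dose changes at T2 may lead to a site visit. The synopsis says that "it is possible to plan a visit on site within the week following phone contact for obtaining new bottles of treatment". Footnote 7 of the Part 2 schedule is more specific: for one step down, "an unscheduled visit should be planned within the week following the phone contact in order to decrease the dose from 20 to 10 mg". Other decreases need no visit.

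**The concern.** All four statements are current text and describe the same call, which comes after V10 and before V11 and allows the dose to be adjusted. They give two dates a week apart. Section 5.2 is where a site looks up what to do at each contact, so the odd date is an operative instruction and not background.

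The stake is when tolerance is first checked after the step at V10. Some patients may go above 20 mg/day there for the first time in the open-label titration, and those who had been on placebo have not had pitolisant in this trial before that titration. If 5.2.12 is followed, the check comes a week later than the other three places intend. Whichever date a site uses, its call is also a deviation under part of the protocol.

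**Working it through.** The protocol derives no T2 date, so there is no figure to reproduce. The check compares the stated days and their windows.

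**Inputs.** V10 = D84 ± 2 (section 5.2.13). T2 = D98 ± 1 (section 5.2.12), or D91 ± 1 (synopsis, Part 2 schedule; section 4.2 gives D91 without a window). V11 = D112, with ± 7 in the synopsis, the Part 2 schedule and section 5.2.14, but ± 2 in section 4.2.

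**1. Can the tolerance reconcile the dates?**
- 91 ± 1 gives D90 to D92.
- 98 ± 1 gives D97 to D99.
- There is no common day. The nominal gap is 98 − 91 = 7 days.

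**2. Does visit order decide between them?** No. Both dates lie after V10 (D84) and before V11 (D112).

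**3. Which date has more support?** D91 appears in three places and D98 in one.

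**4. Time from V10 to the first scheduled check.**

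| | T2 at D91 | T2 at D98 |
|---|---|---|
| Nominal | 91 − 84 = 7 days | 98 − 84 = 14 days |
| Shortest, with windows | 90 − 86 = 4 days | 97 − 86 = 11 days |
| Longest, with windows | 92 − 82 = 10 days | 99 − 82 = 17 days |

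**5. Follow-on visit for a decrease from 20 to 10 mg (within a week of the call).** The nominal last day is 91 + 7 = D98 or 98 + 7 = D105, which is 14 or 21 days after a V10 held on D84. Allowing one day for the T2 window, the last day is D99 or D106.

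**6. With the correction.** Section 5.2.12 then agrees with the other three places. T2 falls 7 days after V10 and 112 − 91 = 21 days before V11.

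**The case against.** The strongest reply is that this matters little. T2 is one phone call in the open-label part. It is not the only safety route, because section 9.1 says that the investigator can be reached by telephone. Patients under 40 kg cannot exceed 20 mg/day at V10. The 40 mg dose was already available from V4 in the double-blind period, so some patients randomised to pitolisant may have taken it before. Many sites may work from the schedule table and call at D91 anyway. All of this stands and limits the size of the point, but none of it reconciles the dates.

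A reader might also infer more than the documents support:

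- **That D98 cannot work because the follow-on visit collides with V11.** With V11 at ± 7 its window opens at D105, so a week ending at D104 to D106 can touch it. With the ± 2 in section 4.2 the window is D110 to D114 and there is no overlap. Even with ± 7, the visit can be held before D105.
- **That D98 breaks a fixed pattern.** D91 is V8 + 28 days, which matches the +14, +21, +28 rhythm of the double-blind visits. The protocol nowhere says that the open-label schedule mirrors them, so this is consistent with D91 but does not prove it.
- **That the T2 dose rules also conflict.** Section 4.2 and the schedule's footnotes say how to handle a decrease. The synopsis, the study treatment section and 5.2.12 give a general re-adjustment rule that is compatible with that.
- **That placing 5.2.12 before V10 (5.2.13) is a second error.** It is section order only.

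**Conclusion.** The inconsistency is real, and section 5.2.12 is wrong as written or the other three places are. The count of three against one makes D91 the likely intended date. No redaction or text-extraction fault explains the difference.

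The size is a nominal 7-day delay, from 7 to 14 days after V10, in the first scheduled tolerance and dose check, plus avoidable off-window calls. The point is minor. It should not be read as a threat to the trial's results: SAP section 3.2 limits the SAP to the blind part, and T2 comes after V8, so no planned double-blind analysis is affected.

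The conclusion assumes that all four places mean the same call, which their content supports. It also assumes that the sponsor will confirm D91 as the intended day.

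**What to change.** In section 5.2.12, change the T2 date from D98 (± 1 day) to D91 (± 1 day), after the sponsor has confirmed it. The T2 dates in the synopsis, the Part 2 schedule and section 4.2 stay as they are. This does not clear those places on other matters: the V11 tolerance in section 4.2, for example, still differs from the ± 7 days given elsewhere.

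The cost is one corrected date and a note to sites, with no added visit, procedure or data item. Moving the T2 section after V10 would help the reader, but it is optional and editorial and would swap two section numbers.

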5.2.13. V10- Dose adjustment visit (Day 84 ± 2 days)

Idem to the visit V9.

Investigational treatment allocation: the dose of pitolisant will be individually adjusted

according to the investigator's prescription.

A blood sample will be taken for routine haematological and biochemical test (including β-

HCG pregnancy test for pubescent female) and semi-quantitative urinalysis (dipstick),

Dose allocation: either 5, 10, 15, 20, 30 or 40 mg/day or placebo in the morning during 28 days.

Patients with a weight less than 40 kg could be treated with a maximum daily dose up to 20 mg.

5.2.14. V11- Dose adjustment visit (Day 112 \pm 7 days)

Idem to the visit V9.

Dose allocation: either 5, 10, 15, 20, 30 or 40 mg/day or placebo in the morning during 3-month.

Patients with a weight less than 40 kg could be treated with a maximum daily dose up to 20 mg.

5.2.15. V12- Dose adjustment visit (Day 196 ± 7 days)

Idem to the visit V11.

Dose allocation: either 5, 10, 15, 20, 30 or 40 mg/day or placebo in the morning during 6-month.

Patients with a weight less than 40 kg could be treated with a maximum daily dose up to 20 mg.

5.2.16. V13- Dose adjustment visit (Day 364± 7 days)

Idem to the visit V12.

A blood sample will be taken for routine haematological and biochemical test (including β-

HCG pregnancy test for pubescent female) and semi-quantitative urinalysis (dipstick),

Dose allocation: either 5, 10, 15, 20, 30 or 40 mg/day or placebo in the morning during 6-month.

Patients with a weight less than 40 kg could be treated with a maximum daily dose up to 20 mg.

All subsequent visits are performed each 6 months as V13.

The investigator should instruct each patient to report any subsequent event(s) that the patient

or his personal physician believes might reasonably be related to participation of this study.

In case of occurrence of adverse event or in case of unresolved adverse event, the investigator

should schedule an additional follow-up in order to follow any adverse events until they are

resolved. Thereafter, the patient will be discharged from the study.

5.2.17. Early withdrawal visit (Open label phase)

The premature withdrawal patients from the study should be followed by a visit performed

within a maximum of 5 days after the last dose of study drug.

Tests and exams are applied as V13 with no dispensation.

Patients will be followed under usual practice after their study discontinuation.

5.2.18. Phone visits during the COVID-19 pandemic

During the COVID-19 pandemic, while patients are unable to attend any visit in the

investigative sites and to limit the risk for the patient to spread/acquire the infection, special

measures are put in place to maintain the participants in the study. During that period and until

return to normal situation at sites, study visits at can be replaced by phone visits.

The investigator should assess during these calls the efficacy and tolerance and the dose of

treatment should be adjusted accordingly, when applicable.

Direct shipment of study treatment from the site, or hospital pharmacy, to the patient's home is

allowed via a courier with the full documentation of shipment and receipt by the patient/parents.

Patients will return all medication at his/her subsequent site visit. Diaries to be documented

daily are sent to the patient with the study treatment.

Protocol P11-06/ BF2.649 EudraCT number: 2013-001506-29

PATIENT WITHDRAWAL CRITERIA 5 3

5.3.1. Criteria to withdraw subject from the trial treatment

In accordance with the Declaration of Helsinki, patients will be free to withdraw from the study at any time if they wish to do so, for any reason specified or unspecified.

Before the final scheduled study visit the investigator have the responsibility and the right to interrupt the patient participation. Out of emergency cases (listed below), the investigator will have to contact the sponsor or his representative before the application of his decision.

- Voluntary withdrawal of patient consent, or loss to follow-up, or inability to remain under medical observation
- Severe depression indicated by Childhood Depression Inventory (CDI \geq 16) or suicidal risk with a positive Columbia-Suicide Severity Rating Scale (C-SSRS).
- Non-compliance or major deviation from the protocol
- Appearance of a Serious Adverse Event (SAE) or any other situation where, in the opinion of the investigator, continuation of the study would not be in the interest of the subject.

Should any of the patients be withdrawn from the study, the reason for withdrawal has to be recorded in the CRF for all withdrawn patients.

5.3.2. Type and timing of data to be collected from withdrawn patients

When a patient is prematurely withdrawn from the study before the "End of study visit" V8, the investigator has to perform a complete visit, within a maximum of 5 days after the last dose of study drug. This will also apply for open label phase.

5.3.3. The follow -up for withdrawn patients

The investigator should make every effort to contact the prematurely withdrawn patient and to identify the reason why he fails to attend the visit and to determinate his health status. In case of adverse event no recovered at the time of study withdrawal, the investigator will have to plan a follow-up visit in order to complete the adverse events evolution.

5.4. STUDY DISCONTINUATION CRITERIA

5.4.1. Criteria for terminating the trial

Bioprojet reserves the right to terminate the study but intends only to exercise this right for valid scientific or administrative reasons, and reasons related to protection of patients. In all cases the Ethics Committee (IRB/IEC) and Health Authorities should be informed.

Possible reason for the study termination can include but are not limited to:

- The discovery of an unexpected, significant or unacceptable risk to patients enrolled in the study
- A decision on the part of Bioprojet to suspend or discontinue the development of the investigational product
- Request of the relevant regulatory agency

If the study is prematurely discontinued, enrolled patients should be called for an "end of study" visit"

5.4.2. Criteria for terminating site

Bioprojet reserves the right to terminate the study at a given centre at any time after the study initiation if:

- ICH GCP regulations are not observed
- The protocol is violated without justification
- The data generated are of poor quality
- Changes in personnel or facilities adversely affect performance of the study (e.g. low rate of inclusion).

6. SAFETY ASSESSMENT AND REPORTING

6.1. **DESCRIPTION OF SAFETY PARAMETERS**

6.1.1. Vital signs

Vital signs including systolic and diastolic blood pressures, heart rate and body weight will be measured at each visit. Measurements will be recorded in the CRF.

6.1.2. Physical examination

A complete physical examination (including the height at screening only) will be performed at screening visit (V1, or V0 when applicable) and at each visit for the purpose to observe the child's overall appearance, general health, and behavior. The examination includes cardiovascular, respiratory, abdominal, neurological, locomotive and dermatologic systems. Any significant abnormalities should be recorded in the CRF.

Version 3.0

EudraCT number: 2013-001506-29

